## CLINICAL TRIAL PROTOCOL SUMMARY

Name of Sponsor:	Zydus Discovery DMCC [name]
Name of Investigational product:	Saroglitazar Magnesium 2 mg and 4 mg
Name of active ingredient of investigational product	Saroglitazar Magnesium
Name of the comparator drug	Placebo
Name of active ingredient of comparator product	Placebo
Potential Indication	Treatment of Non-alcoholic Steatohepatitis
Study Subjects	Patients with Non-alcoholic Steatohepatitis
Number of subjects	15
Number of site(s)	Multicenter
Study Number:	SARO.17.004
Planned treatment Period	24 Weeks
Study Duration	32Weeks
Title of study: A Phase 2, Prospective, Randomized, Double-blind, Placebo-controlled Study to Evaluate the Safety and Efficacy of Saroglitazar Magnesium 2 mg and 4 mg in Patients with Non-alcoholic Steatohepatitis.	
Clinical phase: Phase 2	

Primary Objective:
 
To evaluate the changes in NAFLD Activity Score (NAS) at week 24 from baseline and with no worsening of fibrosis in NASH patients.
 
Secondary Objectives:
 
 
• To evaluate the percentage of responders in the treatment groups.
 
• To evaluate the percentage of responders, defined as the disappearance of steatohepatitis over the time period up to Week 24.
 
• Changes from baseline to Week 24 in Saroglitazar Magnesium 2 mg and 4 mg for the following parameters: 
 
○ Stage of steatosis, lobular inflammation and ballooning.
 
○ Stages of fibrosis.
 
○ Liver function tests (alanine aminotransferase, aspartate aminotransferase, alkaline phosphatase, Gamma-glutamyl transferase, direct bilirubin, total proteins and albumin).
 
○ Lipid profile parameters (triglyceride, small dense low density lipoprotein, high density lipoprotein, low density lipoprotein, very low density lipoprotein, total cholesterol and non HDL cholesterol Apo lipoprotein A1 and Apo lipoprotein B).
 
○ Insulin resistance and glycemic control parameters (fasting plasma glucose, glycosylated hemoglobin, fasting insulin, C-peptide, adiponectin, homeostasis model assessment beta and homeostasis model assessment for insulin resistance).
 
 
 
	

	Approved by: [name] [name]	Protocol No.: SARO.17.004.02.PROTOCOL Version No.: 2.0
--	------------------------------------	---

 Zydus Discovery DMCC	CLINICAL TRIAL PROTOCOL Saroglitazar Magnesium – Phase 2 SARO.17.004	CONFIDENTIAL Page 4 of 76
--	---	--

- To assess the safety of Saroglitazar Magnesium in patients with non-alcoholic steatohepatitis over 24 weeks of treatment.

**Criteria for Safety:**

- Frequency and severity of adverse events
- Physical examination and body weight
- Vital signs
- Clinical laboratory testing (hematology, clinical chemistry, serology and urinalysis).
- 12-lead electrocardiogram (ECG).

**Criteria for inclusion/exclusion:**

**INCLUSION CRITERIA**

1. Patients able to provide written informed consent for participation in this trial.
2. Males or females, 18 to 75 years of age, both inclusive.
3. Female must be either of non-child bearing potential (surgically sterilized at least 6 months prior to screening or postmenopausal) or using one or more methods of contraception.
4. Histologic confirmation of NASH without cirrhosis (fibrosis stage 0, 1, 2, or 3) from liver biopsy performed either during the screening period or no more than 6 months prior to the first visit, with a NAS of  $\geq 4$  and a score of at least 1 in each (steatosis scored 0-3, ballooning scored 0-2, and lobular inflammation scored 0-3). If biopsy was performed within 6 months of screening, the slides, biopsy material or block should be available for baseline documentation. Such patients, whose historical biopsy report is available, should not use medications suspected of having an effect on NASH for at least 3 months prior to the screening.
5. BMI  $\geq 25$  kg/m^2.
6. For hypertensive patients, blood pressure must be controlled by a stable dose of antihypertensive medications for at least 3 months prior to screening (and the stable dose can be maintained throughout the study)
7. Patients with type 2 diabetes mellitus may be included if they fulfil the following criteria:
  - a. Stable therapeutic regimen as defined by no changes in oral agents or dose for at least 3 months before screening and the stable dose can be maintained throughout the study.
  - b. HbA1c  $\leq 9.5\%$
8. Patients agree to comply with the study procedure.

**EXCLUSION CRITERIA**

1. Pregnant and lactating female.
2. Positive pregnancy test.
3. Patients with history of myopathies or evidence of active muscle diseases.
4. Patients with history of alcohol consumption of  $>30$  gm/day for men,  $>20$  gm/day for women for consecutive previous 2 years and/or drug abuse.
5. Known allergy, sensitivity or intolerance to the study drug or formulation ingredients.
6. Participation in an interventional clinical study and/or receipt of any investigational medication within 3 months prior to screening.
7. History of malignancy in the past 5 years and/or active neoplasm with the exception of superficial, non-melanoma, skin cancer.

	Approved by: [name] [name]	Protocol No.: SARO.17.004.02.PROTOCOL Version No.: 2.0
--	------------------------------------	---

8. Any of the following laboratory values at screening:
  - a. Direct bilirubin >1.5 mg/dL,
  - b. Serum albumin <2.5 g/dL.
  - c. Estimated glomerular filtration rate (eGFR) <60 mL/min/1.73m^2.
  - d. Serum alanine aminotransferase (ALT) or aspartate aminotransferase (AST) >200 IU/L.
  - e. Patient with international normalized ratio (INR) >1.5.
  - f. Creatinine kinase ≥ 1.5 ULN.
  - g. Lipase ≥ULN.
  - h. Amylase ≥ ULN.
9. Unstable cardiovascular disease, including:
  - a. unstable angina, (i.e., new or worsening symptoms of coronary heart disease within the 3 months preceding screening), acute coronary syndrome within the 6 months preceding Screening, acute myocardial infarction within the 3 months preceding screening or heart failure of New York Heart Association class (III – IV) or worsening congestive heart failure, or coronary artery intervention, within the 6 months preceding screening
  - b. history of (within 3 months preceding Screening) or current unstable cardiac dysrhythmias
  - c. uncontrolled hypertension (systolic blood pressure [BP] > 155 mmHg and/or diastolic BP > 95 mmHg)
  - d. Stroke or transient ischemic attack within the 6 months preceding screening.
10. Previous history of bladder disease and/or hematuria.
11. Previous liver biopsy that demonstrated presence of cirrhosis or radiologic imaging consistent with cirrhosis or portal hypertension.
12. Type 1 diabetes mellitus.
13. Use of drugs that are known CYP2C8 inhibitors/substrate.
14. Use of drugs associated with a clinical or histological picture consistent with fatty liver disease or NASH for more than 12 consecutive weeks in the 1 year prior to start of the study; (these include amiodarone, tamoxifen, methotrexate, glucocorticoids, anabolic steroids, tetracyclines, estrogens, valproate/valproic acid, chloroquine, anti-HIV drugs).
15. History of thyroid disease (hypothyroid patients who are euthyroid on thyroid hormone replacement can be included).
16. History of, or current, cardiac dysrhythmias.
17. History of bariatric surgery, or undergoing evaluation for bariatric surgery.
18. Patients with a >10% weight loss in the 3 months prior to screening.
19. History or other evidence of severe illness or any other conditions that would make the patient, in the opinion of the Investigator, unsuitable for the study (such as poorly controlled psychiatric disease, coronary artery disease, HIV or active gastrointestinal conditions that might interfere with drug absorption).
20. Patients on any treatment with other drugs used for treatment of NASH [pentoxifyllin, ursodeoxycholic acid, antioxidants such as vitamin E (>800 IU/day), glutathione, orlistat, betaine, incretin mimetics or non-prescribed complementary alternative medications (including dietary supplements, megadose vitamins, herbal preparations and special teas)] or any medicine in clinical trials for NASH. *(However, patients who are taking stable dose of vitamin E for at least 3 months prior to screening will be enrolled in the study).*
21. History of other causes of chronic liver disease [autoimmune, primary biliary cirrhosis, hepatitis B virus (HBV) and hepatitis C virus (HCV), Wilson disease, alpha-1-antitrypsin deficiency, hemochromatosis etc.

 Zydus Discovery DMCC	CLINICAL TRIAL PROTOCOL Saroglitazar Magnesium – Phase 2 SARO.17.004	CONFIDENTIAL Page 6 of 76
--	---	--

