Following confirmation of inclusion/exclusion criteria and upon histological confirmation of NASH by liver biopsy, patients will be enrolled into the study.

Eligible patients will be randomly assigned to receive Saroglitazar Magnesium 2 mg or 4 mg or placebo in a 2:2:1 ratio for 24 weeks.

Upon completion of 24 weeks of treatment, liver biopsy will be performed and the NAFLD Activity Score recorded (Appendix 2).

	Approved by: [name] [name]	Protocol No.: SARO.17.004.02.PROTOCOL Version No.: 2.0
---	---	---

 Zydus Discovery DMCC	CLINICAL TRIAL PROTOCOL Saroglitazar Magnesium – Phase 2 SARO.17.004	CONFIDENTIAL Page 7 of 76
--	---	--

The scheduled visits during this study will be as follows:

- Visit 1: Screening Visit [-4 Week (-28 Days)],
- Visit 2: Enrollment Visit (Day 1± 7 Days /Week 0),
- Visit 3: Day 43/Week 6 ± 7 Days,
- Visit 4: Day 85/Week 12 ± 7 Days,
- Visit 5: Day 127/Week 18 ± 7 Days,
- Visit 6: Day 169/Week 24 ± 7 Days,
- Visit 7: Follow-up Visit: Day 197/Week 28 ± 7 Days,

If the patient has consumed restricted medications but is otherwise considered eligible to be enrolled in this study by the PI, a minimum of 1 month wash out period will be instituted before the screening visit. All unscheduled visits will be reported in the Case report form.

Patients will be advised to follow a stable lifestyle. No change in the intensity of lifestyle (Diet/Exercise) will be allowed during the period of study. Patient will be monitored for safety and efficacy parameters as per Visit Schedule.

If further investigations are required in case of any AE, Investigator is advised to assess the AE and take necessary action. Patients are advised to contact the Investigator for any complaints.

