## 1 STUDY FLOW CHART

*NOTE: Liver biopsy showing NASH within 6 months preceding Visit 1 can be used.*

 Zydus Discovery DMCC	CLINICAL TRIAL PROTOCOL Saroglitazar Magnesium – Phase 2 SARO.17.004	CONFIDENTIAL Page 20 of 76
---	---	---

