## 2 INTRODUCTION

### 2.1 MEDICAL BACKGROUND

Non-alcoholic fatty liver disease (NAFLD) is a condition characterized by hepatic steatosis in the absence of a history of significant alcohol use or other known liver disease. Its progressive form is called Non-alcoholic steatohepatitis (NASH). This metabolic disorder occurs mainly in overweight or obese individuals, but recently NASH is emerging as one of the main causes of chronic liver disease. NASH is considered to be the hepatic component of the metabolic syndrome, which includes obesity, hyperinsulinemia, peripheral insulin resistance, diabetes, dyslipidemia and hypertension. NASH has been thought to be the precursor for many of the idiopathic liver cirrhosis. The pathogenic mechanism involves hyperinsulinemia and hepatic insulin resistance, hepatic fat accumulation (steatosis) and a “second hit” of oxidative stress producing inflammation and leading to fibrosis. But the actual succession of events in progression of NAFLD to NASH and cirrhosis is still poorly understood [1].

The general criteria for histological diagnosis of NASH generally include steatosis, hepatocyte injury in the form of ballooning and lobular inflammation. Hepatocyte injury can take the form of ballooning, apoptosis, or lytic necrosis. Ballooning is a major feature of NASH [2]. Furthermore ballooning has been associated with poor prognosis and severe ballooning has been correlated with higher incidence of cirrhosis [3]. Lobular inflammation is usually mild and consists of mixed inflammatory cells including lymphocytes, eosinophils and neutrophils. Scattered Kupffer cell aggregates are also common.

The prevalence of NAFLD and NASH has been major cause of liver disease worldwide. However, given the trends in the prevalence of diabetes and obesity, the prevalence of NAFLD and its consequences are expected to increase in the near future [4].

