#### 4.3 EXCLUSION CRITERIA

1. Pregnant and lactating female.
2. Positive pregnancy test.
3. Patients with history of myopathies or evidence of active muscle diseases.
4. Patients with history of alcohol consumption of  $>30$  gm/day for men,  $>20$  gm/day for women for consecutive previous 2 years and/or drug abuse.
5. Known allergy, sensitivity or intolerance to the study drug or formulation ingredients.
6. Participation in an interventional clinical study and/or receipt of any investigational medication within 3 months prior to screening.
7. History of malignancy in the past 5 years and/or active neoplasm with the exception of superficial, non-melanoma, skin cancer.
8. Any of the following laboratory values at screening:
  - a. Direct bilirubin  $>1.5$  mg/dL
  - b. Serum albumin  $<2.5$  g/dL
  - c. Estimated glomerular filtration rate (eGFR)  $<60$  mL/min/1.73m^2
  - d. Serum alanine aminotransferase (ALT) or aspartate aminotransferase (AST)  $>200$  IU/L
  - e. Patients with international normalized ratio (INR)  $>1.5$
  - f. Creatinine kinase  $\geq 1.5$  ULN

	Approved by: [name] [name]	Protocol No.: SARO.17.004.02.PROTOCOL Version No.: 2.0
--	------------------------------------	---

 Zydus Discovery DMCC	CLINICAL TRIAL PROTOCOL Saroglitazar Magnesium – Phase 2 SARO.17.004	CONFIDENTIAL Page 29 of 76
--	---	---

- g. Lipase  $\geq$ ULN
  - h. Amylase  $\geq$  ULN.
9. Unstable cardiovascular disease, including:
- a. unstable angina, (i.e., new or worsening symptoms of coronary heart disease within the 3 months preceding screening), acute coronary syndrome within the 6 months preceding Screening, acute myocardial infarction within the 3 months preceding screening or heart failure of New York Heart Association class (III – IV) or worsening congestive heart failure, or coronary artery intervention, within the 6 months preceding screening
  - b. history of (within 3 months preceding Screening) or current unstable cardiac dysrhythmias
  - c. uncontrolled hypertension (systolic blood pressure [BP] > 155 mmHg and/or diastolic BP > 95 mmHg)
  - d. Stroke or transient ischemic attack within the 6 months preceding screening.
10. Previous history of bladder disease and/or hematuria.
11. Previous liver biopsy that demonstrated presence of cirrhosis or radiologic imaging consistent with cirrhosis or portal hypertension.
12. Type 1 diabetes mellitus.

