### 5.8.4 Other Restrictions

#### 5.8.4.1 Alcohol

Subjects are encouraged to stop alcohol consumption entirely during the study. They are not permitted to consume >1 unit of alcohol per day (>7 units per week) during the study. Alcohol consumption will be recorded throughout the study period.

	Approved by: [name] [name]	Protocol No.: SARO.17.004.02.PROTOCOL Version No.: 2.0
---	------------------------------------	---

 Zydus Discovery DMCC	CLINICAL TRIAL PROTOCOL Saroglitazar Magnesium – Phase 2 SARO.17.004	CONFIDENTIAL Page 41 of 76
---	---	---

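### Exclusion 4's two-year alcohol wording can admit recent heavy drinkers, who must then cut down on study, and the SAP does not use the alcohol data

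*Protocol*

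**What the plan says.** **Entry.** Criterion 4, in the Protocol synopsis and again in Section 4.3, opens "Patients with history of alcohol consumption of" more than 30 g/day for men and ends, after the 20 g figure, "gm/day for women for consecutive previous 2 years and/or drug abuse". No other criterion limits alcohol. Criterion 19 (investigator judgement) and criterion 21 (other chronic liver disease, an open-ended list) do not name it. Section 2.1 describes NAFLD as "hepatic steatosis in the absence of a history of significant alcohol use or other known liver disease".

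**Other look-backs.** Criterion 14 excludes drugs associated with fatty liver or NASH when used for more than 12 consecutive weeks in the preceding year. Criterion 18 looks back 3 months for weight loss.

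**On study.** Section 5.8.4.1 says "Subjects are encouraged to stop alcohol consumption entirely during the study", then "They are not permitted to consume >1 unit of alcohol per day (>7 units per week) during the study", then "Alcohol consumption will be recorded throughout the study period". It does not give the grams in a unit.

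**Baseline histology.** The flow-chart section states "NOTE: Liver biopsy showing NASH within 6 months preceding Visit 1 can be used".

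**Analysis.** The primary endpoint is the change in NAS at Week 24 without worsening of fibrosis. ALT, AST and GGT changes are secondary (SAP 6.2). SAP 6.4 plans descriptive summaries by arm, t-tests and Fisher's exact tests against placebo for listed secondary endpoints, and treatment differences with 95% intervals. None is adjusted for a covariate. The SAP describes no use of the alcohol data, and alcohol is not among the baseline characteristics named in SAP Section 5.

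**The concern.** Alcohol is the exposure that the protocol's own description of NAFLD sets aside, yet its look-back is the loosest of those compared above. A patient whose steatohepatitis is partly alcohol-related can pass criterion 4 and then be told to cut down or stop. NAS, steatosis, ALT, AST and GGT could then fall without any drug effect.

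This is a descriptive trial with 6, 6 and 3 patients, so within-arm changes and responder percentages carry much of the message. One such patient is visible in an arm's result, and no planned table would let a reader see why.

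**Working it through.** **1. The plan's own figure.** 15 patients at 2:2:1 gives 15 × 2/5 = 6, 15 × 2/5 = 6 and 15 × 1/5 = 3, as stated in Protocol 8.4 and SAP Section 4. There is no power calculation to reproduce.

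**2. What criterion 4 lets through.** The intake of 60 g/day below is illustrative, for a man.
- Literal reading (excess throughout the 2 years): 60 g/day for the last 18 months is not excluded, because 18 < 24 months.
- Two-year average: 60 g/day for the last 9 months after none gives 60 × 9/24 = 22.5 g/day, below 30, so he is not excluded.
- At any time in the 2 years: he is excluded. The text does not say this.

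**3. Entry limit against on-study limit.** The grams per unit, u, are an assumption (8 to 14). The ratio is limit/u, and the cut for a patient exactly at the entry limit is (limit − u), as a share of the limit.

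| u (g) | Men: 30/u | Cut, men | Women: 20/u | Cut, women |
|---|---|---|---|---|
| 8 | 3.75 | 22 g/day (73%) | 2.50 | 12 g/day (60%) |
| 10 | 3.00 | 20 g/day (67%) | 2.00 | 10 g/day (50%) |
| 12 | 2.50 | 18 g/day (60%) | 1.67 | 8 g/day (40%) |
| 14 | 2.14 | 16 g/day (53%) | 1.43 | 6 g/day (30%) |

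Every ratio exceeds 1. A properly admitted patient may therefore have to cut down, but only one who drinks more than 1 unit/day.

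**4. Leverage of one patient.** Suppose one patient has an alcohol-related NAS fall of d = 1 to 3 points (assumption). The arm mean moves by d/n:
- n = 6: 1/6 = 0.17 to 3/6 = 0.50.
- n = 3: 1/3 = 0.33 to 3/3 = 1.0.

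One extra responder is 1/6 = 17 percentage points in an active arm or 1/3 = 33 on placebo.

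**5. Chance imbalance.** If k of the 15 are such patients (k assumed), P(none on placebo) = C(12,k)/C(15,k).
- k = 1: 12/15 = 0.80.
- k = 2: 66/105 = 0.63.
- k = 3: 220/455 = 0.48.

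With one or two such patients, the likeliest outcome is that any alcohol-related fall sits only in the active arms. If one does fall on placebo, that arm's mean moves twice as far (d/3 against d/6), which can hide a drug effect.

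**The case against.** The strongest reply is that the alcohol rule is identical in every arm of a randomised, double-blind trial. That stands. A reader might infer a bias in favour of the drug, but none is expected. The exposure is to within-arm change and to chance imbalance. One-patient leverage at 6/6/3 also applies to any prognostic factor. Alcohol differs in that the protocol itself prompts the change.

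Entry is not unguarded. Criterion 21 is open-ended, criterion 19 allows exclusion on judgement, and NASH must be confirmed by a centrally read biopsy. An investigator could also read criterion 4 as covering any time in the two years. These points lower the chance of admitting such a patient. They do not give sites a defined rule, and differing readings across centres are themselves a reason to reword.

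Three further inferences are tempting, and the documents do not support them:
- **Alcohol is missing from the visit schedule.** The visit lists defer to Table 1, which is not in the text available, and 5.8.4.1 says intake is recorded.
- **Exceeding the limit is not a deviation.** The list in Protocol 7.5 is expressly not exhaustive. A violation that may influence the primary endpoint is reportable, and one that affects efficacy evaluation removes the patient from the PP set (Protocol 8.2.1.3, SAP 3.1).
- **The alcohol instruction contradicts the stability rule.** That rule reads "No change in the intensity of lifestyle (Diet/Exercise) will be allowed during the period of study"; it names diet and exercise, and alcohol has its own section.

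Finally, the size of the problem is assumed throughout. The documents do not give the grams per unit, the NAS effect of cutting down, or the number of such patients. The gap between the limits may also be modest for women, at 1.43 times if a unit is 14 g.

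**Conclusion.** The point holds in a limited form and should be acted on. Criterion 4 is loose and ambiguous, the on-study cap lies below the entry limit for both sexes at any assumed unit of 8 to 14 g, and the SAP plans nothing that would show an alcohol-related change. Because the baseline biopsy may predate Visit 1 by up to 6 months, baseline NAS can reflect drinking before the restriction.

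The consequence is possible non-drug improvement in within-arm NAS, ALT, AST and GGT, and noise in the arm differences. Per affected patient the shift is 0.17 to 0.50 NAS points in an active arm or 0.33 to 1.0 on placebo, if the alcohol-related fall is 1 to 3 points. Whether any such patient would enrol cannot be judged from the documents.

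**What to change.** - **Criterion 4, synopsis and Section 4.3.** Keep the gram limits. Reword so that sustained intake above them during any part of the 2 years before the baseline biopsy, or between that biopsy and Day 1, excludes the patient. Define sustained by a window consistent with the protocol's other look-backs, for example the 12 consecutive weeks of criterion 14.
- **Criterion 4 and Section 5.8.4.1.** Express the entry and on-study limits in one unit and reconcile the two passages. Which limit is appropriate is for the sponsor to settle.
- **SAP.** Add a by-arm table of the alcohol data that 5.8.4.1 already promises, at baseline and on study, placed beside the histology and liver-test results. Have influential breaches considered when the PP set is decided, before unblinding.

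The cost is eligibility wording, one table and perhaps a few more screen failures. If enrolment has already closed, the table and the PP review remain feasible.

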**Methodology:**

This is a randomized, double-blind, placebo-controlled study to evaluate safety and efficacy of Saroglitazar Magnesium 2 mg and 4 mg in patients with NASH. This study will be initiated after obtaining the approvals of Institutional Ethics Committee/Institutional Review Board (IEC/IRB) and the local regulatory authority.

It is the responsibility of the Principal Investigator (PI) to ensure that the study is conducted in accordance with the protocol, International Council for Harmonisation Good Clinical Practice and all applicable regulatory requirements. Informed consent will be obtained before the start of any study related procedures.

As per the contemporary guidelines, the Investigator shall maintain Source Documents (SD), Site Master File (SMF), Informed Consent Forms/Documents (ICF/ICD) and other logs/forms during the conduct of a study.

All laboratory reports should be reviewed by the PI and/or his/her designee and any abnormal findings should be addressed. All protocol deviations occurring on the study shall be documented and the Sponsor and IEC/IRB informed.

Patients clinically suspected of NASH will be invited for a screening programme for inclusion in the study. Patients will be screened according to the inclusion and exclusion criteria. Clinical evaluation will be conducted for baseline characteristics and anthropometry measurements such as body weight and height.

After clinical evaluations, all baseline safety and efficacy parameters will be recorded as per Visit Schedule. All laboratory collections will be performed following overnight fasting (at least 8 hrs).

Following confirmation of all clinical and laboratory inclusion and exclusion criteria, patients will continue into the screening period. During the screening period liver biopsy will be performed. However, if a biopsy was performed within 6 months the slides and biopsy material, or block, must be made available for baseline documentation. Such Patients, whose historical biopsy report is available, should not use medication suspected of having an effect on NASH from the 3 months prior to the screening.

Liver biopsy will be performed to confirm the diagnosis of NASH and record a baseline NAFLD Activity Score (Appendix 2). The histological evidence of NASH is defined as NAS  $\geq$  4 with a minimum score of 1 for all of its three components [steatosis, hepatocyte ballooning and lobular inflammation].

Following confirmation of inclusion/exclusion criteria and upon histological confirmation of NASH by liver biopsy, patients will be enrolled into the study.

Eligible patients will be randomly assigned to receive Saroglitazar Magnesium 2 mg or 4 mg or placebo in a 2:2:1 ratio for 24 weeks.

Upon completion of 24 weeks of treatment, liver biopsy will be performed and the NAFLD Activity Score recorded (Appendix 2).

	Approved by: [name] [name]	Protocol No.: SARO.17.004.02.PROTOCOL Version No.: 2.0
---	---	---

 Zydus Discovery DMCC	CLINICAL TRIAL PROTOCOL Saroglitazar Magnesium – Phase 2 SARO.17.004	CONFIDENTIAL Page 7 of 76
--	---	--

The scheduled visits during this study will be as follows:

- Visit 1: Screening Visit [-4 Week (-28 Days)],
- Visit 2: Enrollment Visit (Day 1± 7 Days /Week 0),
- Visit 3: Day 43/Week 6 ± 7 Days,
- Visit 4: Day 85/Week 12 ± 7 Days,
- Visit 5: Day 127/Week 18 ± 7 Days,
- Visit 6: Day 169/Week 24 ± 7 Days,
- Visit 7: Follow-up Visit: Day 197/Week 28 ± 7 Days,

If the patient has consumed restricted medications but is otherwise considered eligible to be enrolled in this study by the PI, a minimum of 1 month wash out period will be instituted before the screening visit. All unscheduled visits will be reported in the Case report form.

Patients will be advised to follow a stable lifestyle. No change in the intensity of lifestyle (Diet/Exercise) will be allowed during the period of study. Patient will be monitored for safety and efficacy parameters as per Visit Schedule.

If further investigations are required in case of any AE, Investigator is advised to assess the AE and take necessary action. Patients are advised to contact the Investigator for any complaints.

